11.5. Efficacy Analyses

The primary endpoint of percentage change in EASI from Baseline to Week 12 will be analyzed in the FAS and using MI procedure with analysis of covariance (ANCOVA) model. The ANCOVA model will include treatment group as factor, Baseline EASI score and randomization factor as covariates. Multiple results of ANCOVA (least square [LS] means and LS mean difference from placebo) for each MI dataset will be analyzed and reported along with 95% confidence interval (CI) and p-value using Rubin's method (██████████).

Proportion-based key secondary endpoints (eg, EASI-75, vIGA 0 to 1) at Week 12 will be analyzed in the FAS using the Cochran-Mantel-Haenszel method adjusted for randomization stratification factor. The number and percentage of subjects achieving the goal and the difference in proportion between treatment groups achieving the goal, along with p-value and the 95% CIs will be reported.

Other secondary endpoints (listed in Section 11.5.4) will be analyzed using the following methods in general and specific details will be discussed in the SAP.

- Longitudinal continuous variables measured at scheduled visits up to Week 12 will be analyzed using a MMRM model. The MMRM model will include treatment group, visit, and interaction of treatment-by-visit as factors, and baseline measure and randomization stratification factor as covariates. An unstructured covariance matrix will be specified for the MMRM model. LS means at visit and LS mean differences between treatment group with p-values and corresponding 95% CIs will be reported. This method will also be applied to other score based or continuous measures.
- Longitudinal dichotomous measures at scheduled visits will be analyzed using a logistic regression model. The model will include treatment group as a factor, Baseline EASI score and randomization stratification factor as covariates. The odds ratios and 95% CIs, and associated p-value will be reported.

Analysis methods for exploratory endpoints will be described in the SAP.

In addition to between group analyses on the primary and secondary endpoints, dose response of key efficacy measures for the 2 etrasimod doses and placebo will be assessed as exploratory using appropriate analysis models, which will be specified in the SAP.

Efficacy data will be analyzed by randomized treatment, while safety data will be analyzed by actual treatment.

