EASI values at scheduled visits up to Week 12 will be analyzed using a MMRM model. The MMRM model will include treatment group, visit, and interaction of treatment-by-visit as factors, baseline EASI and baseline vIGA (3 versus 4) and region [REDACTED] as covariates. An unstructured (UN) covariance matrix will be specified for the MMRM model. If the model does not converge using an unstructured covariance matrix, an auto-regressive AR(1) structure will be tested. If AR(1) fails to converge, a compound symmetric structure will be used. LS means and LS mean differences at each visit between treatment groups with p-values and corresponding 95% CIs will be reported.

The same ANCOVA model as described above for the primary analysis will be performed, using the following:

- Last Observation Carried Forward (LOCF): The primary endpoint will be analyzed in the modified FAS (mFAS), with assessments after the first use of rescue medication set to missing. All missing data will be imputed using post-baseline LOCF method.
- Worst Case Carried Forward (WCCF): The primary endpoint will be analyzed in the mFAS, with assessments after the first use of rescue medication set to missing. All missing data will be imputed using post-baseline WCRF method.
- Observed Cases (OC) in mFAS: observed data analyses in mFAS, regardless of rescue medication uses and without missing data imputation,

will be performed using a mixed effects model with repeated measures (MMRM) including all scheduled visits up to Week 12.

- OC in Per Protocol Set (PPS): observed data analysis will be performed among PPS, regardless of rescue medication uses and without missing data imputation.
- OC in treatment completers (TCS): observed data analysis will be performed among mFAS subjects who have completed 12 weeks of study treatment, regardless of rescue medication uses and without missing data imputation.

C. Key Secondary Efficacy Outcome Analyses

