- Longitudinal continuous variables (percent change in weekly peak pruritus NRS, change and percentage change in %BSA) measured at visits (weeks) up to Week 12 will be analyzed with a MMRM model based on FAS using observed data. The MMRM model will include treatment group, visit (week), and interaction of treatment-by-visit (week) as factors, and baseline measure and randomization stratification factors as covariates. An unstructured covariance matrix will be specified for the MMRM model. If the model does not converge using an unstructured covariance matrix, an auto-regressive AR(1) structure will be tested. If AR(1) fails to converge, a compound symmetric structure will be used. LS means at visit (week) and LS mean differences at visit (week) between treatment group with p-values and corresponding 95% CIs will be reported.
- Dichotomous measures (weekly peak NRS ≥ 3 reduction, EASI-50, and EASI-90) at Week 12 will be analyzed in the same way as for the key secondary endpoints based on FAS with CMH method adjusted for randomization stratification factors of baseline vIGA score (3 versus 4) and region [REDACTED]. Missing data (including those after use of rescue medication) will be handled by NRI method. The number, percentage of subjects achieving the goal and Clopper-Pearson exact 95% confidence intervals will be reported. The differences in proportion between treatment groups, along with p-values and the 95% CIs will also be reported. Weekly peak NRS ≥ 3 reduction will be assessed among the subset of subjects whose baseline peak NRS is ≥ 3 .

Sensitivity analyses will be performed in the PPS and TCS using observed data.

E. Exploratory Efficacy Outcome Analysis

Below exploratory endpoints will be analyzed in a similar manner as the secondary continuous variables with the MMRM model based on FAS using observed data.

- Change in DLQI from Baseline to Week 12.
- Change in POEM from Baseline to Week 12.
- Percent change in SCORAD total and individual symptom scores from Baseline to Week 12.

The primary and sensitivity analysis for all efficacy endpoints are summarized in **Table 3**.

Table 3 Summary of Efficacy Analyses

Efficacy Endpoint	Primary Analysis	Sensitivity Analysis
DB Treatment Period		
Primary		

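### The MMRM gives all visits one baseline slope, so Week 12 absolute change in %BSA, DLQI and POEM can be under-adjusted for baseline and lose precision

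*SAP*

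**What the plan says.** SAP 8.D gives the fixed effects as treatment group, visit and their interaction, "and baseline measure and randomization stratification factors as covariates". It adds: "An unstructured covariance matrix will be specified for the MMRM model", with AR(1) and then compound symmetry as fallbacks if the model does not converge. The secondary endpoints covered are "percent change in weekly peak pruritus NRS, change and percentage change in %BSA".

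SAP 8.E carries the model over to change in DLQI, change in POEM and percent change in SCORAD: "Below exploratory endpoints will be analyzed in a similar manner as the secondary continuous variables with the MMRM model".

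Protocol 11.5 has the same specification: "The MMRM model will include treatment group, visit, and interaction of treatment-by-visit as factors, and baseline measure and randomization stratification factor as covariates".

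The observed-case EASI MMRM in SAP 8.B has the same form: "interaction of treatment-by-visit as factors, baseline EASI and baseline vIGA (3 versus 4) and region".

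Neither document has a baseline-by-visit interaction. Treatment is allowed a different effect at each visit, but baseline is not.

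**The concern.** Each of these endpoints is a Week 12 quantity, but the baseline coefficient is estimated jointly over Weeks 1, 2, 4, 6, 8 and 12. For an absolute change, little has moved by Week 1 and the change is nearly unrelated to the starting value. By Week 12 there has been more time for improvement and for regression toward the mean, so subjects who start higher fall further. If the slope really differs by visit, a single slope is a compromise. An unstructured covariance weights that compromise toward the early visits, where change from baseline varies least. The Week 12 contrast then receives less baseline adjustment than the data could support.

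At stake is the width of the Week 12 confidence intervals. The plan reports estimates and intervals in an exploratory manner, so precision is the main thing these analyses deliver.

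**Working it through.** **Plan's own figure.** The documents give no power or efficiency figure for the MMRM endpoints. The only sample size calculation is for the primary endpoint: difference 35, SD 41, one-sided 0.025, power at least 90%. An exact two-sample t-test needs 30 per arm (power 90.2%), and 30/(1 − 0.25) = 40 per arm, which matches the plan. I therefore use about 30 evaluable per arm below.

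**Formula.** Let β_t be the slope of change on baseline at visit t, R the between-visit covariance given baseline, and R12 the Week 12 variance in R. Under an unstructured covariance with complete data, the common slope is

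b_c = (1′R⁻¹β) / (1′R⁻¹1).

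The share of Week 12 precision lost, relative to a model with baseline-by-visit, is

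1 − R12 / [R12 + (β12 − b_c)² · var(B)].

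**Inputs.** The visits are those in SAP 4.E. Every correlation below is an assumption. Variances are set equal and scaled to 1, so β12 = ρ − 1 and R12 = 1 − ρ², where ρ is the baseline-to-Week-12 correlation.

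**One case in full: AR(1) decay, ρ = 0.5.** The visit slopes run −0.06, −0.11, −0.21, −0.29, −0.37, −0.50. The common slope is −0.09, about 18% of what Week 12 needs. With R12 = 0.75 and (−0.50 + 0.09)² = 0.168, the loss is 1 − 0.75/0.918 = 18%. Omitting baseline altogether would lose 25%.

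**Other patterns, absolute change:**

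| Assumed correlation pattern | ρ = 0.3 | ρ = 0.5 | ρ = 0.7 |
|---|---|---|---|
| Constant (compound symmetry) | 0% | 0% | 0% |
| AR(1) + 20% visit-level error | 9% | 5% | 1% |
| AR(1) + 10% visit-level error | 15% | 10% | 4% |
| AR(1) | 23% | 18% | 12% |
| Linear decay | 29% | 21% | 13% |

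At ρ = 0.5 the common slope is −0.21 with 10% error and −0.30 with 20% error, against −0.50 needed. That is about 42% and 61% of the adjustment.

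**Simulation check** (30 and 40 per arm, 4,000 trials per setting, ρ = 0.5): AR(1) loss 18-20%, with 10% error 10-11%, with 20% error 4%, constant correlation nil.

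**Percent change.** With lognormal scores and ρ = 0.5 (40 per arm, 3,000 trials), the losses were about 0% under constant correlation, 4% and 8% with 20% and 10% error, and 13% under AR(1). AR(1) at ρ = 0.3 gave 14%. If reduction is simply proportional to baseline, percent change is nearly unrelated to baseline and the loss is negligible.

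**Translation.** A loss l multiplies interval width by 1/√(1 − l). A 5% loss gives 1.03 and acts like 28.5 of 30 evaluable subjects per arm. A 20% loss gives 1.12 and acts like 24 of 30.

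**The case against.** Four points on the other side have weight.

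- **The size is assumed.** The documents give no between-visit correlation, no visit-level error and no SD for these endpoints. A reader might infer that Week 12 is almost unadjusted, with a firm 10-20% loss. Near-total under-adjustment occurs only when decay is close to AR(1) or linear. With modest visit-level error, 40-80% of the adjustment is made, and with constant correlation all of it. This objection stands.
- **Many MMRM endpoints are percent changes.** Weekly peak NRS, one of the two %BSA endpoints and SCORAD are percent changes, and the effect on these is small or absent. This stands and narrows the point to absolute change in %BSA, DLQI and POEM. For EASI, the text of SAP 8.B models EASI values while Table 3 lists percent change. If raw values are modelled, the absolute-change figures apply, because subtracting baseline shifts every slope by the same 1.
- **Validity is not in question.** A reader might infer that chance baseline imbalance biases the Week 12 estimate. Under randomization with complete data the estimate is unbiased and its standard error already covers chance imbalance, so this is the same efficiency loss and not a second harm. Baseline vIGA is also a stratification factor and a covariate. With dropout related to baseline, a misspecified slope could in principle bias the result, but the documents give only a dropout rate of up to 25%, with no pattern from which to claim it.
- **Little rests on these models.** The primary analysis is a Week 12 ANCOVA with its own baseline slope, the key secondary endpoints use CMH, and no error rate is controlled. This limits the importance but does not make the common-slope model preferable.

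**Conclusion.** The point holds as a cheap gain in precision. The term is absent throughout, and the mechanism is real for absolute change whenever correlation with baseline decays, which is plausible over 12 weeks in a disease that the protocol describes as relapsing and remitting. The Week 12 loss for change in %BSA, DLQI and POEM is 0% to about 29%, roughly 5-20% under moderate decay. For percent-change endpoints it is about 0-13%. These ranges rest on assumed correlations, equal variances and complete data.

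The documents do not support reading this as a flaw in the primary or key secondary analyses, or as a source of bias under randomization with complete data.

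**What to change.** In SAP 8.D and 8.E, add a baseline-by-visit interaction to the MMRM for absolute change in %BSA, DLQI and POEM. Add it to the EASI MMRM in 8.B for consistency, so that this sensitivity analysis, like the primary ANCOVA, has a Week 12 baseline slope. For percent change in weekly itch it is optional: the 12-week unstructured covariance already has 12 × 13/2 = 78 parameters, and a single baseline-by-continuous-week term would be lighter than 11 separate ones.

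The cost is one model term, five extra parameters for the six clinic visits, and no new data. If the slopes prove constant, only a few degrees of freedom are lost.

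Timing matters. SAP section 1 provides for finalization before unblinding, with later amendment for labelled ad hoc analyses, and section 12 already describes post hoc work with subject counts by treatment group. If the data are already unblinded, keep the planned model as specified and report the interaction model beside it as a labelled additional analysis.

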It is assumed that the percent change in EASI from Baseline to Week 12 will be normally distributed with an estimated standard deviation (SD) of 41%. Assuming a 1:1:1 randomization, 120 subjects (40 subjects each in 1 mg etrasimod, 2 mg etrasimod, and placebo groups) is sufficient to achieve at least 90% power to detect a difference of 35% in EASI from Baseline to Week 12 between each of the etrasimod treatment groups and placebo by a 2-sample t-test using a 1-sided significance level of 0.025. This sample size also accounts for an estimated drop-out rate up to 25%.

D. Treatment Randomization

Randomization will be stratified by vIGA score at Baseline (3 versus 4) and region

E. Assessment Schedule

For the statistical analysis, DB Treatment Period will include 12 weeks treatment and 4 weeks safety follow-up; OLE Period will include 52 weeks treatment and 4 weeks safety follow-up. The date at which the subject is randomized will be referred to as the “Baseline/Day 1”. Subjects will be requested to attend the following scheduled visits for the DB Treatment Period from their Baseline/Day 1 visit: Week 1, 2, 4, 6, 8, 12 and Week 16/SFU visit. For the OLE Period, Week 16 (this will be same as Week 16 in the DB Treatment Period), Week 17, 18, 20, 24, 28, 32, 40, 48, 56, 68, and Week 72/ SFU. The acceptable visit window for scheduled visits for the DB Treatment Period including Week 16, and Week 17 and 18 in OLE Period is ± 3 days, for all the other OLE visits, the scheduled visit window is ± 7 days. Visits that subjects make to the clinic outside the visit window are recorded as unscheduled visits.

Please refer to protocol for details.

5. General Analytical Considerations

A. Data Sources and General Rules

Data are recorded on electronic case report form (eCRF) for each subject screened/enrolled in this study. These forms will be used to transmit information collected during the study to the Sponsor and regulatory authorities, as applicable. Laboratory data, [REDACTED] blood samples and [REDACTED] data are collected separately by the selected vendors. Section 14 of the protocol provides additional details regarding data handling and record keeping.

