Statistical analysis will be performed following IQVIA Biotech standard operating procedures and on the IQVIA Biotech computer network. All statistical analysis will be performed using SAS Version 9.4 with program code prepared specifically for the project by qualified IQVIA Biotech statisticians and SAS programmers.

All observed and derived variables (e.g., change from baseline, percentage change from baseline, and response status) that are analyzed or summarized will be listed by subject. Descriptive statistics will provide an overview of the efficacy and safety results. For categorical parameters, the number and percentage of subjects in each category will be presented. For continuous parameters, descriptive statistics will include number of subjects, mean, SD median, minimum, and maximum.

B. Definition of Baseline and Study Day

Study day will be defined separately for the DB Treatment Period and OLE Period. For all subjects, Day 1 is the date of first study drug administration in the DB Treatment Period. This will be referred to as the **Overall Day 1**. For those enrolling into the OLE Period, an **OLE Day 1** will be additionally defined as the date of the first study drug administration in the OLE Period at Week 16.

Study day will be calculated relative to the date of Overall Day 1.

Similarly, Baseline will be defined separately for DB Treatment Period and OLE Period as follows:

[figure not shown]
- **DB Treatment Period:** baseline will be defined as the last available measurement prior to the first dose of the study drug in DB Treatment Period. Specifically, for vital signs (resting heart rate (HR), blood pressure (BP), body temperature, and respiratory rate) and [REDACTED], the Day 1 pre-randomization assessments will be used as baseline measurements. The lowest pre-dose HR measurement will be used for comparison to the post-dose HR measurement. This will be referred to as the **DB baseline**.

[figure not shown]
- OLE Period: for those enrolling into the OLE Period, an **OLE baseline** will be additionally defined as the last pre-dose measurement at Week 16 at Week 16.

Change from baseline is defined for both DB Treatment Period and OLE Period as the post-baseline value minus the baseline value unless otherwise specified. Percent change from baseline is calculated as follows: Percent change = (Change from baseline / Baseline) x 100.

C. Analysis Visit Window

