- **Pruritus NRS** is a simple assessment tool of the intensity of pruritus (itch) from 0 to 10 with 0 being “no itch” and 10 being “the worst itch imaginable.” Both maximum/peak and average NRS scores will be assessed.

In a daily diary, subjects are asked to rate their worst itch and itch on average over the previous 24 hours. The weekly average NRS (peak and average) will be analyzed as efficacy endpoints, and derived as per the following schedule and rule:

- For DB Treatment Period: Baseline (Day 1), Week 1 (Day 2 to 8), Week 2 (Day 9 to 15), Week 3 (Day 16 to 22)...Week 12 (Day 79 to 85)... and Week 16 (Day 107 to Day 113 or Day of Week 16 visit whichever comes first for subjects enrolled into OLE Period).
- For OLE Period: Week 17 (Day of week 16 visit +1 to Day 120), Week 18 (Day 121 to 127), Week 19 (Day 128 to 134)...Week 28 (Day 191 +).
- Subjects must complete at least 3 NRS entries to calculate the weekly average. The weekly average will be considered missing if more than 4 entries are missing for that weekly interval. The baseline for the analysis of diary data is Day 1.

At each scheduled office visit, the subject is asked to rate their worst itch and itch on average in the past 7 days and these are recorded as office based peak and average NRS.

- **BSA AD** will be assessed for each region of the body and combined. The region percent affected BSA is the affected percentage (0-100) at each body region. The total percent affected BSA is the sum of multiplying region percent affected BSA by the multiplication factor with a maximum of 100.

Body Region	Multiplication Factor
Head and Neck	9%
Upper Limbs (right)	9%
Upper Limbs (left)	9%
Lower Limbs (right)	18%
Lower Limbs (left)	18%
Anterior Trunk	18%
Back	18%
Genitals	1%

- **PGA** includes 2 questions **for wellness and appearance**. Subjects will rate their overall well-being based on a 5-point Likert scale from poor to excellent. Response choices are: ‘Poor’, ‘Fair’, ‘Good’, ‘Very Good,’ or ‘Excellent’.

- **POEM** consists of 7 questions asking patients to rank how many days over the past 7 days they have experienced specific AD-related symptoms. Each of the seven questions carries equal weight and is scored from 0 to 4 as follows:

No days	Scored 0
1-2 days	Scored 1
3-4 days	Scored 2
5-6 days	Scored 3
Every day	Scored 4

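### If the unstructured MMRM does not converge, the SAP falls back to structures with one variance for all visits, so the Week 12 standard error is wrong whenever variability differs by visit

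*SAP*

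**What the plan says.** SAP 8.D analyses the continuous secondary endpoints (percent change in weekly peak pruritus NRS, change and percent change in BSA) by MMRM. The first choice is clear: "An unstructured covariance matrix will be specified for the MMRM model". Then: "If the model does not converge using an unstructured covariance matrix, an auto-regressive AR(1) structure will be tested", and finally "If AR(1) fails to converge, a compound symmetric structure will be used". SAP 8.B gives the same sequence for the observed-case EASI MMRM, a sensitivity analysis of the primary endpoint. SAP 8.E analyses the exploratory endpoints in a similar way, and SAP 12.A and 12.C reuse these models post hoc. Protocol 11.5 names the unstructured matrix only.

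For each visit or week, "LS mean differences at visit (week) between treatment group with p-values and corresponding 95% CIs will be reported". Neither SAP section names a heterogeneous-variance structure, an empirical standard error or a degrees-of-freedom method. SAP 5.A fixes the software: "All statistical analysis will be performed using SAS Version 9.4".

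SAP 4.E schedules the double-blind clinic visits at "Week 1, 2, 4, 6, 8, 12 and Week 16/SFU visit", which is six post-baseline visits up to Week 12. SAP 8.A derives the diary itch score weekly, which is 12 time points.

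**The concern.** The unstructured matrix gives Week 12 its own variance. In SAS, AR(1) and CS are the equal-variance forms; the versions with a variance per visit have other names (ARH(1), CSH). The SAP does not use the words equal variance; this follows from the standard meaning of the terms in the named software.

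Once one variance is pooled over visits, the Week 12 standard error reflects all visits. If change from baseline spreads as treatment proceeds, the calmer early visits pull it down and the Week 12 interval is too narrow. Separately, AR(1) works on visit order, so the four weeks from Week 8 to Week 12 get the same correlation as the one week from Week 1 to Week 2.

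Week 12 is the visit named in these endpoints. The plan reports estimates and intervals without formal testing, so the accuracy of the interval is what a reader relies on.

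**Working it through.** **The plan's own figure.** The documents state no number for the MMRM covariance. Their only SD is 41, for percent change in EASI at Week 12, in the sample-size statement (difference 35, at least 90% power, "by a 2-sample t-test using a 1-sided significance level of 0.025"). That statement reproduces: with 30 per arm the noncentrality is 35/(41 × √(2/30)) = 3.31 and power is 90.2%; 30/0.75 = 40 per arm, 120 in total.

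**Formula.** With complete data and arm-by-visit means, a compound-symmetry fit estimates its one variance as the mean of the visit variances. In large samples:

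- SE ratio r = √(mean visit variance) / (SD at Week 12)
- coverage of a nominal 95% interval = 2Φ(1.96 r) − 1

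Only the shape of the SD profile matters, not its scale. Every profile below is an assumption that ends at 41.

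| SD by visit | Mean variance | r | Coverage |
|---|---|---|---|
| 20, 24.2, 28.4, 32.6, 36.8, 41 | 981.7 | 31.33/41 = 0.764 | 86.6% |
| 30, 32.2, 34.4, 36.6, 38.8, 41 | 1274.4 | 35.70/41 = 0.871 | 91.2% |
| 30, 37, then 41 at four visits | 1498.8 | 38.71/41 = 0.944 | 93.6% |
| 20, 27, 34, then 41 (12 diary weeks) | 1451.2 | 38.09/41 = 0.929 | 93.1% |
| 41 throughout | 1681 | 1.000 | 95.0% |

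If the SD instead falls by a third over the period, r is about 1.3 and coverage about 99%: the intervals are too wide.

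**AR(1).** This is the step more likely to be used, because a structure with two parameters seldom fails. Its large-sample error is close to that of compound symmetry. With six visits, the SD doubling linearly in calendar weeks and lag-1 correlation 0.5 to 0.85, r is 0.73 to 0.76 for AR(1) and 0.73 for compound symmetry. The latter is below the 0.764 in the table mainly because growth there is linear in visit order. For growth of 1.5 times, the ratios are 0.82–0.83 and 0.81.

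**Dropout.** Simulation with 40 per arm, 25% random monotone dropout, lag-1 correlation 0.7, model-based standard errors and 1,000 runs:

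| SD growth | Structure | Model SE | Empirical SE | Coverage |
|---|---|---|---|---|
| 1.5× | AR(1) | 8.30 | 10.34 | 88.8% |
| 1.5× | CS | 8.10 | 10.43 | 87.5% |
| 2× | AR(1) | 7.39 | 10.40 | 83.0% |
| 2× | CS | 7.16 | 10.52 | 81.3% |

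**Does the remedy work?** In a second simulation of the same design (500 runs), plain AR(1) covered 86.8% (1.5×) and 85.8% (2×). Heterogeneous AR(1) covered 95.0% and 93.6%, and AR(1) with a sandwich standard error 94.2% and 93.6%.

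**How likely is the trigger?** The unstructured matrix has 6 × 7/2 = 21 parameters for the clinic-visit models and 12 × 13/2 = 78 for the diary model. In simulated normal data with 40 per arm, an unstructured REML fit converged in 300 of 300 runs for six visits (25% dropout). For 12 weeks it converged in 300 of 300 with 25% dropout and 5% intermittent missingness, and in 298 of 300 with 40% dropout, 15% intermittent missingness and correlation 0.95. This was a purpose-written optimiser, not PROC MIXED, and the result has not been repeated. The models for individual body regions, SCORAD symptoms, and the per-protocol and completer sets were not tried.

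**The case against.** The strongest objection is that the rule will hardly ever be used. A reader might infer that 78 covariance parameters from about 120 subjects will defeat the unstructured fit. The documents do not show this: 120 subjects over 12 weeks give up to 1,440 values, and the convergence check points the other way. That stands for the main models. It is weaker for the sparse ones. SAP 5.B divides by baseline, so percent change is undefined for a body region or symptom scored zero at baseline, and the per-protocol and completer sets are smaller.

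Second, the SD profile is assumed. Protocol 3.2 chose 12 weeks so that the drug could reach its full effect and hold it for a time, which makes a plateau plausible; the loss is then one to two percentage points of coverage. This also stands. So does the point that the unequal-spacing fault applies only to the clinic visits, not to the weekly diary, and that no size has been put on it.

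Third, nothing decisive depends on these models. SAP 5.F controls no type I error, and the EASI MMRM is one of seven sensitivity analyses in Table 3. That limits the priority, but does not make a wrong interval right.

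**Conclusion.** The point holds as a conditional one. If the unstructured fit fails, the prescribed fallback gives a wrong Week 12 standard error whenever variance differs by visit. Under compound symmetry with complete data, coverage runs from about 87% (SD 20 to 41) through 91% (30 to 41) and about 93% (early rise, then plateau) to 95% (equal variances), and exceeds 95% if the SD falls. Dropout can lower coverage further. These figures rest on assumed SD profiles and on default model-based standard errors.

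A reader might go further and conclude that the Week 12 intervals in this trial are too narrow. The documents do not support that: they give no SD by visit, they do not say that any model fell back, and the direction of the error depends on the profile.

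The effect is confined to secondary, exploratory, sensitivity and post hoc MMRM results. The primary ANCOVA with multiple imputation and the CMH analyses are unaffected. This is a low-priority improvement.

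**What to change.** In SAP 8.B and 8.D, replace the fallback order with structures that keep a variance per visit: heterogeneous Toeplitz, then ARH(1), then heterogeneous compound symmetry. Alternatively, keep simpler structures but use empirical (sandwich) standard errors with any structure other than unstructured. Either way, state the degrees-of-freedom method and report which structure each model used.

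The cost is SAP wording and a PROC MIXED option. The downsides are small. Heterogeneous Toeplitz needs 12 + 11 = 23 covariance parameters for the diary model and ARH(1) needs 12 + 1 = 13, against two for AR(1). Sandwich standard errors are slightly liberal at 40 per arm (93.6% to 94.2% coverage above).

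Timing matters. SAP Section 12 already contains post hoc analyses with counts by arm, so this version appears to post-date unblinding, and a new order could not be called prespecified for double-blind results already produced. If a model has already fallen back, add the rerun as a labelled ad hoc analysis, which SAP Section 1 allows before the final database lock. If none has, a statement that every MMRM converged with the unstructured matrix settles the point.
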